3.3.2 Inclusion criteria

For inclusion in the study volunteers must fulfill all of the following criteria:

1. Provision of signed written informed consent, ability to communicate with the investigator, and to understand and comply with the requirements of the study
2. Males and females aged 18-65, inclusive
3. Body Mass Index (BMI) 18-29 inclusive. BMI will be calculated as weight in kilogram (kg)/height in meters² (m²).
4. Women who are surgically sterilized, post-menopausal for at least one year, or not pregnant and/or lactating. Women of childbearing potential must be willing to abstain from sexual activity or use an effective double barrier method of contraception during the study period (e.g., condom and diaphragm, condom and foam, condom and sponge, etc.), or intrauterine devices

5. Chinese and Japanese volunteers must have parents of the same reported race. (See Section 4.1.1.1)
6. Residence in the United States for at least 12 months.

For inclusion in the genetic component of the study, volunteers must fulfill the following criterion:

1. Provision of signed written informed consent for genetic research

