3.4.3 Method of assigning volunteers to treatment groups

Written informed consent will be obtained before enrollment. Each volunteer will be assigned a unique enrollment number that will begin with E0001101 for Chinese volunteers, E0001201 for Japanese volunteers, and E0001301 for Caucasian volunteers.

Volunteers fulfilling the eligibility criteria and continuing in the study will be assigned unique randomization codes (subject numbers) that will begin with 1101 for Chinese volunteers, 1201 for Japanese volunteers, and 1301 for Caucasian volunteers.

Volunteers will be assigned enrollment/randomization codes strictly sequentially as they enroll/are eligible for randomization. If a volunteer discontinues from the study the randomization/subject number will not be re-used and the volunteer will not be allowed to re-enter the study. It is important to note that enrollment numbers and subject numbers may not match and careful observation must be made when documenting study information and identifying treatment sequences.

Volunteers will be randomized within each ethnic group according to a randomization scheme that will be generated by the biostatistics group at AstraZeneca.

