4.1 Medical examination and demographic measurements

4.1.1 Enrollment medical examination and demographic measurements

Each volunteer will undergo an enrollment medical examination and screening in the 35 days prior to Day -1A (screening period). This will consist of:

- Recording of demographic data - date of birth, sex, race (See Section [4.1.1.1](#))
- A standard medical history and a physical examination including the cardiovascular and respiratory systems
- A blood sample for standard clinical chemistry and hematology assessments a mid-stream urine sample for urinalysis and drugs of abuse screen
- A blood sample for serology (HIV, HbsAg, Hepatitis C)
- A resting blood pressure and heart rate measurement.
- A serum pregnancy test (for women of child-bearing potential)
- A 3-day dietary assessment (See Section [4.1.1.4](#))

- An electrocardiogram (ECG)

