4.1.1.2 Medical History and Complete Physical Exam

A complete medical and drug history will be recorded for each volunteer at the initial screening visit and reviewed for any additions or omissions on admission to the CRC (Day – 1A). Significant medical conditions that have occurred within the past 2 years, or conditions that are ongoing (i.e., headache, backache, indigestion) are to be recorded in the CRF. The drug history must identify any known drug allergies, presence or history of drug abuse, and use of chronic medications.

The complete physical examination will include an assessment of the following:

- General appearance,
- Skin, head, neck, and lymph nodes
- Musculoskeletal/extremities (including spine)
- Cardiovascular
- Lungs
- Abdomen
- Neurological (reflexes)

Physical examination data to be recorded on the CRF will include: 1) normal/abnormal and 2) a description of any abnormalities.

Height in centimeters (cm) and weight in kg will be measured at screening only and will be recorded on the CRF.

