6.4.4 Methods of statistical analyses

All demographic and baseline data, including medications, will be listed and summarized using standard summary statistics for continuous variables and frequency counts and percentages for categorical variables.

Pharmacokinetic data, C_{\max} , $AUC_{(0-t)}$, and AUC, $t_{1/2z}$, λ_z and CL/F, of each study medication will be summarized for each ethnic group using descriptive statistics, including geometric means and coefficient of variation, and listed. In addition, 95% confidence intervals (CI) for the mean pharmacokinetic parameters will also be presented. Time to peak plasma concentration, t_{\max} , will be summarized using the median value and range for each ethnic group.

Log-transformed C_{\max} , $AUC_{(0-t)}$, and AUC will be analyzed using a mixed model with the fixed effect of ethnicity, sequence, treatment, and period and random effect subject. Appropriate contrasts and their 90% CIs will be produced from the model, these estimates will then be anti-log transformed to obtain the geometric means and their 90% CIs for the

quantities of interest. In addition, 95% confidence intervals (CI) for the mean pharmacokinetic parameters will also be presented.

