enterohepatic recirculation. Mean plasma elimination half-life of atorvastatin in humans is approximately 14 hours, but the half-life of inhibitory activity for HMG-CoA reductase is 20 to 30 hours due to the contribution of active metabolites. Less than 2% of a dose of atorvastatin is recovered in urine following oral administration.

Special Populations

Geriatric: Plasma concentrations of atorvastatin are higher (approximately 40% for C_{max} and 30% for AUC) in healthy elderly subjects (age >65 years) than in young adults. Clinical data suggest a greater degree of LDL-lowering at any dose of drug in the elderly patient population compared to younger adults (see PRECAUTIONS section; Geriatric Use subsection).

Pediatric: Pharmacokinetic data in the pediatric population are not available.

Gender: Plasma concentrations of atorvastatin in women differ from those in men (approximately 20% higher for C_{max} and 10% lower for AUC); however, there is no clinically significant difference in LDL-C reduction with LIPITOR between men and women.

Renal Insufficiency: Renal disease has no influence on the plasma concentrations or LDL-C reduction of atorvastatin; thus, dose adjustment in patients with renal dysfunction is not necessary (see DOSAGE AND ADMINISTRATION).

Hemodialysis: While studies have not been conducted in patients with end-stage renal disease, hemodialysis is not expected to significantly enhance clearance of atorvastatin since the drug is extensively bound to plasma proteins.

Hepatic Insufficiency: In patients with chronic alcoholic liver disease, plasma concentrations of atorvastatin are markedly increased. C_{max} and AUC are each 4-fold greater in patients with Childs-Pugh A disease. C_{max} and AUC are approximately 16-fold and 11-fold increased, respectively, in patients with Childs-Pugh B disease (see CONTRAINDICATIONS).

Clinical Studies

Prevention of Cardiovascular Disease

[figure not shown]

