Following an oral dose of ¹⁴C-labeled simvastatin in man, 13% of the dose was excreted in urine and 60% in feces. Plasma concentrations of total radioactivity (simvastatin plus ¹⁴C-metabolites) peaked at 4 hours and declined rapidly to about 10% of peak by 12 hours postdose. Since simvastatin undergoes extensive first-pass extraction in the liver, the availability of the drug to the general circulation is low (<5%).

¹ Registered trademark of MERCK & CO., Inc.
COPYRIGHT © 1999-2005 MERCK & CO., Inc.
All rights reserved

Both simvastatin and its η -hydroxyacid metabolite are highly bound (approximately 95%) to human plasma proteins. Rat studies indicate that when radiolabeled simvastatin was administered, simvastatin-derived radioactivity crossed the blood-brain barrier.

The major active metabolites of simvastatin present in human plasma are the η -hydroxyacid of simvastatin and its 6 β -hydroxy, 6 β -hydroxymethyl, and 6 β -exomethylene derivatives. Peak plasma concentrations of both active and total inhibitors were attained within 1.3 to 2.4 hours postdose. While the recommended therapeutic dose range is 5 to 80 mg/day, there was no substantial deviation from linearity of AUC of inhibitors in the general circulation with an increase in dose to as high as 120 mg. Relative to the fasting state, the plasma profile of inhibitors was not affected when simvastatin was administered immediately before an American Heart Association recommended low-fat meal.

In a study including 16 elderly patients between 70 and 78 years of age who received ZOCOR 40 mg/day, the mean plasma level of HMG-CoA reductase inhibitory activity was increased approximately 45% compared with 18 patients between 18-30 years of age. Clinical study experience in the elderly (n=1522), suggests that there were no overall differences in safety between elderly and younger patients (see PRECAUTIONS, *Geriatric Use*).

Kinetic studies with another reductase inhibitor, having a similar principal route of elimination, have suggested that for a given dose level higher systemic exposure may be achieved in patients with severe renal insufficiency (as measured by creatinine clearance).

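### The ethnic groups are observational and not balanced by design on sex or age, yet the model in 6.4.4 has no subject covariates; a supportive sex- and age-adjusted analysis should be fixed in advance

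*Protocol*

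**What the plan says.** The model is stated in the protocol synopsis and again in 6.4.4: log-transformed Cmax, AUC(0-t) and AUC are fitted "with the fixed effect of ethnicity, sequence, treatment, and period", with subject random. No characteristic of the volunteer other than ethnicity enters. Demographic data are listed and summarised only.

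Randomisation concerns the order of the drugs. Section 3.4.3 says: "Volunteers will be randomized within each ethnic group according to a randomization scheme". Ethnic group is self-reported (4.1.1.1). Eligibility in 3.3.2 is wide: "Males and females aged 18-65, inclusive" and "Body Mass Index (BMI) 18-29 inclusive". No matching, quota or stratification by sex or age is stated.

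The covariates will be available. Section 4.1.1 lists "Recording of demographic data - date of birth, sex, race", and 4.1.1.2 adds that "weight in kg will be measured at screening only".

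Two quantities depend on the ethnic comparison. The primary objective (2.1) compares each Asian group with Caucasians for each drug. Section 6.4.2 makes the primary question a ratio of those ethnic ratios, atorvastatin or simvastatin against rosuvastatin.

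The appended labels describe sex and age effects. Appendix D: "Plasma concentrations of atorvastatin in women differ from those in men (approximately 20% higher for C_{max} and 10% lower for AUC". The same section gives higher atorvastatin exposure over age 65 than in young adults (Cmax about 40%, AUC about 30%). Appendix E, for patients aged 70 to 78 on simvastatin, says that "inhibitory activity was increased approximately 45% compared with 18 patients between 18-30 years of age".

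**The concern.** The crossover makes each volunteer his or her own control between drugs, not between ethnic groups. A per-drug Asian/Caucasian ratio is a comparison of different people, so any difference in their sex or age mix that affects exposure is read as ethnicity.

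The ratio of ratios is better protected, because a covariate effect shared by all three drugs cancels within the volunteer. An effect that differs between drugs does not cancel. It would appear as a difference between statins in the size of the ethnic effect, which is the question in 6.4.2. The atorvastatin label shows that such an effect is plausible. An adjustment chosen only after an imbalance has been seen would carry less weight than one fixed beforehand.

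**Working it through.** **The plan's own figure.** Section 6.4.5 gives 27 per group for AUC (limits 0.70 to 1.43, true ratio 1, power 90%) but no variability, so 27 cannot be reproduced independently. Reading the 90% interval as two one-sided 5% tests, it can be back-solved with a normal approximation:

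- log margin m = ln(1/0.7) = 0.357
- SD of the within-volunteer log difference = m / (1.645 + 1.645) × √(27/2) = 0.398
- standard error of the ratio of ratios = 0.398 × √(2/27) = 0.108

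The power and error figures below rest on this SD, which is also assumed for Cmax.

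**Which terms matter.** Let volunteer i in ethnic group g have log exposure on drug d equal to a drug mean, plus an ethnic effect for that drug, plus β_d × (1 if female), plus subject and period effects. Let Δp be the difference between two ethnic groups in the share of women.

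- Per-drug ethnic ratio: multiplied by exp(β_d × Δp).
- Ratio of ratios, atorvastatin (A) over rosuvastatin (R): multiplied by exp((β_A − β_R) × Δp).

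A sex main effect imposes one β on all drugs, so β_A − β_R = 0 and the second quantity cannot move. Simulated data (27 per group, three complete periods) agree. Adding sex as a main effect left the ratio-of-ratios estimate unchanged to five decimals in all 5 runs. With 18 of 27 against 9 of 27 women, an atorvastatin AUC sex ratio of 0.90 and a true ratio of ratios of 1, the expected unadjusted value is 0.90^(9/27) = 0.965. Over 300 runs the mean was 0.957 unadjusted and 0.989 with sex crossed with treatment (Monte Carlo error 0.006 to 0.007). The SD of the log estimate rose from 0.106 to 0.115.

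**Size of the sex effect.** Inputs: label ratios 1.20 (Cmax) and 0.90 (AUC), women to men; β_R = 0, an assumption because the documents give no sex effect for rosuvastatin; Δp = 0.30, hypothetical, about 8 of 27 volunteers.

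- Cmax: 1.20^0.30 = 1.056, or +5.6%. Share of log margin: 0.0547 / 0.357 = 15%.
- AUC: 0.90^0.30 = 0.969, or -3.1%. Share of log margin: 0.0316 / 0.357 = 9%.

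These directions apply if the Asian group has more women; with more Caucasian women the factors invert. The same factors apply to the atorvastatin per-drug ethnic ratio, with no assumption about rosuvastatin.

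| Gap in share of women | AUC factor | Power | Cmax factor | Power |
|---|---|---|---|---|
| 10 points | 0.990 | 0.898 | 1.018 | 0.895 |
| 20 points | 0.979 | 0.894 | 1.037 | 0.881 |
| 30 points | 0.969 | 0.886 | 1.056 | 0.857 |
| 50 points | 0.949 | 0.860 | 1.095 | 0.783 |

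If the true ratio sat exactly on a limit and a 30-point imbalance pulled the estimate toward 1, the 5% false-equivalence rate would become 8.8% (AUC) or 12.7% (Cmax).

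**Age.** Both label contrasts use groups above the eligible maximum of 65. Spreading them log-linearly over an assumed 40 years (atorvastatin) or 50 years (simvastatin), a 10-year gap in mean age gives 1.30^(10/40) = 1.068 (atorvastatin AUC), 1.40^(10/40) = 1.088 (atorvastatin Cmax) and 1.45^(10/50) = 1.077 (simvastatin). These are extrapolations. The simvastatin figure is enzyme inhibitory activity, whereas the trial assays simvastatin and simvastatin acid by LC/MS/MS.

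**The case against.** The best defence is that 6.4.1 announces a comprehensive SAP, and covariate-adjusted sensitivity analyses usually belong there. An unadjusted primary model is also a legitimate choice when the question is whether exposure differs between populations as they are. Comparability is partly controlled: one centre, a BMI range, at least 12 months of US residence, no chronic prescription medication, standard in-patient meals. The synopsis has demographics summarised by ethnic group, so an imbalance would be visible.

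Much of this stands. The unadjusted analysis can remain primary, and the lack of a sensitivity analysis in the protocol would not by itself be a fault. But the protocol does more than defer: it fixes the model, twice, without subject covariates for a non-randomised factor. A table that shows an imbalance does not say what it did to the ratios.

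Stronger readings are tempting, and the documents do not support them:

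- *That the ratio of ratios is biased.* This needs an actual imbalance and an effect that differs from rosuvastatin's. The documents show neither.
- *That age acts differently on the drugs.* The two label age effects run in the same direction and are of broadly similar size, and none is given for rosuvastatin.
- *That body weight is a known source of error.* No weight effect on exposure is given for any of the three drugs, and an effect common to all three would cancel in the ratio of ratios.
- *That a shift in a per-drug ratio can be judged against 30%.* That margin belongs to the ratio of ratios; no margin is set for per-drug ratios.

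**Conclusion.** The point holds in a limited form. The per-drug ethnic ratios are open to confounding by sex and age, and the ratio of ratios is open to it where an effect is drug-specific. The fixed model offers no check, although the data will be in hand.

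The only documented effect that applies to the eligible population is atorvastatin in women. Its consequence is modest: about 15% (Cmax) or 9% (AUC) of the log margin at a 30-point sex gap, and nothing if the groups are balanced. This rests on the label ratios at face value, no rosuvastatin sex effect, and a gap that is illustrative. The age figures are suggestive only. The size justifies a planned supportive analysis, not a change of primary analysis.

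**What to change.** In 6.4.4, or in the SAP with a reference from 6.4.4:

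1. Keep the unadjusted analysis as primary, and add the ethnicity-by-treatment term. Without it the listed model holds every ratio of ratios at 1, so the 6.4.2 contrasts cannot be estimated.
2. Pre-specify one supportive model that adds sex and age, each crossed with treatment. Report its per-drug ratios and ratios of ratios beside the unadjusted ones. Main effects alone would adjust the per-drug ratios but, with complete three-period data, leave the ratios of ratios unchanged.
3. Treat a further version with body weight crossed with treatment as optional and exploratory, because it may remove the part of the ethnic effect that runs through body size.

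The cost is a few lines of text and one more model run; no new data or volunteers are needed. With three drugs, each covariate adds one main effect and two interaction coefficients, six in all for sex and age. Intervals in the supportive analysis may be somewhat wider: in the simulation above, sex alone raised the SD by about 9% (0.115 / 0.106 = 1.085).

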6.4.5 Determination of sample size

For AUC, using the equivalence margin of 30% (0.7 to 1.43), an expected ratio of 1, and 90% power to conclude equivalence, the sample size for each group is 27. Approximately 30 volunteers will be recruited to each ethnic group.

6.5 Interim analyses

Not applicable

6.6 Data monitoring committee

Not applicable

7. ETHICS

7.1 Ethics review

The final study protocol, including the final version of the Informed Consent Form, must be approved or given a favorable opinion in writing by an IRB as appropriate. The investigator must submit written approval to AstraZeneca before he or she can enroll any volunteer into the study.

The principal investigator is responsible for informing the IRB of any amendment to the protocol in accordance with local requirements. In addition, the IRB must approve all advertising used to recruit volunteers for the study. The protocol must be re-approved by the IRB annually, as local regulations require.

The principal investigator is also responsible for providing the IRB with reports of any serious and unexpected adverse drug reactions from any other study conducted with the investigational product. AstraZeneca will provide this information to the principal investigator.

Progress reports and notifications of serious and unexpected adverse drug reactions will be provided to the IRB according to local regulations and guidelines.

For the genetic aspect of this study, approval must be obtained for this genetic research and the associated genetic informed consent from the IRB. It must be clearly stated in the approval that this genetic research is approved. The investigator must submit written approval to AstraZeneca before any volunteer participates in this genetic research.

7.2 Ethical conduct of the study

The study will be performed in accordance with the ethical principles that have their origin in the Declaration of Helsinki and are consistent with GCP, applicable regulatory requirements and the AstraZeneca policy on Bioethics.

7.3 Informed Consent

The principal investigator will ensure that the volunteer is given full and adequate oral and written information about the nature, purpose, possible risk and benefit of the study. Volunteers must also be notified that they are free to discontinue from the study at any time. The volunteer should be given the opportunity to ask questions and allowed time to consider the information provided.

The volunteer's signed and dated informed consent must be obtained before conducting any procedure specifically for the study.

The principal investigator must store the original, signed Informed Consent Form. A copy of the Informed Consent Form must be given to the volunteer.

If modifications are made according to local requirements, the new version has to be approved by AstraZeneca.

To participate in the genetic component of the study the volunteer must sign and date both the consent form for the main study (non-genetic components of the study) and the genetic component of the study. Copies of both signed and dated consent forms must be given to the volunteer and the original filed at the study center. The principal investigator(s) is responsible for ensuring that consent is given freely and that the volunteer understands that they may freely discontinue the genetic aspect of the study at any time.

If modifications are made according to local requirements, the new version has to be approved by AstraZeneca.

7.4 Subject data protection

The Master Informed Consent Form will incorporate (or, in some cases, be accompanied by a separate document incorporating) wording that complies with relevant data protection and privacy legislation. Pursuant to this wording, volunteers will authorize the collection, use and disclosure of their study data by the investigator and by those persons who need that information for the purposes of the study.

The Master Informed Consent Form will explain that study data will be stored in a computer database, maintaining confidentiality in accordance with national data legislation. All computer processed data by AstraZeneca may be identified by study code, enrollment codes, randomization codes, and/or initials.

The Master Informed Consent Form will also explain that for data verification purposes, authorized representatives of AstraZeneca, a regulatory authority, or an IRB/Ethics Committee may require direct access to parts of the hospital or practice records relevant to the study, including volunteers' medical history.

All data protection and confidentiality principles, described in the main study protocol, are applicable to this genetic research.

Reference to participation in this genetic research should not be recorded into the volunteers' general medical records. All notes should be kept within the clinical study records.

Due to the exploratory nature of this genetic research, there will be no routine communication of results to volunteers. AstraZeneca will not provide individual genotype results to volunteers, any insurance company, any employer, their family members, general physician or any other third party, unless required to do so by law.

Extra precautions are taken to preserve confidentiality and prevent genetic data being linked to the identity of the volunteer, however, it must be recognized that there are exceptional circumstances where individuals may see both genetic data and a volunteer's personal identifier, for example in the case of a medical emergency, when AstraZeneca physicians and investigators might know the volunteers' identity and might have access to the genetic data, or during regulatory audit where designated authorities must be permitted access to the relevant files.

